### **Loss of PASI 75 response over time**

The loss of PASI 75 response will be repeated, but not truncated at Week 68 and subjects who did not lose PASI 75 response up to Week 68 will not be considered as censored. In addition, the secukinumab treatment groups will also be compared, i.e. a Cox proportional hazards regression will be fitted as described above including all four treatment groups. Placebo (secukinumab 150 mg in core studies) and Placebo (secukinumab 300 mg in core studies) will be compared as well as secukinumab 150 mg and secukinumab 300 mg.

### **Loss of IGA 0 or 1 response over time**

Loss of IGA 0 or 1 response over time will be analyzed analogously to the loss of PASI 75 response, but it will be restricted to the subset of subjects who have been IGA 0 or 1 responder at Week 52.

### **PASI score over time**

Summary statistics will be provided for absolute PASI scores as well as for percent change from baseline by visit and treatment group. Figures will also be provided.

### **IGA mod 2011 score over time**

Summary statistics for the IGA mod 2011 score over time will be presented by visit and treatment group in contingency tables.

### **Relapse**

Relapse will be analyzed analogously to loss of PASI 75 response. Additional analyses will be performed for relapses observed in the follow-up period.

### **Rebound**

Rebound is defined as a worsening of PASI of > 125% of the value at baseline (core study), or new pustular, erythrodermic or more inflammatory psoriasis occurring within 8 weeks of stopping therapy (i.e., if this definition is fulfilled at more than 8 weeks after last study treatment administration, this is not defined as rebound). The number and percentage of subjects experiencing rebound will be presented by visit and treatment group.

## **Subjects who were re-treated after relapse with secukinumab 150 mg or 300 mg**

### **Time to PASI 75 response**

Kaplan-Meier estimates including 95% confidence intervals for cumulative rate of subjects gaining PASI 75 response after relapse will be calculated (time point of re-initiation of secukinumab therapy will be defined as time zero).

### **Time to IGA 0 or 1 response**

Time to IGA 0 or 1 response will be analyzed analogously to time to PASI 75 response but limited to the subset of subjects who were not IGA 0 or 1 responder at time of relapse.

### **PASI 50, PASI 75, PASI 90, PASI 100 and IGA 0 or 1 response over time**

Summary statistics for PASI 50, PASI 75, PASI 90, PASI 100 and IGA 0 or 1 response by visit after relapse will be presented in contingency tables and will include absolute and relative frequencies. Confidence intervals for response rates will be derived as well based on the score method including continuity correction ([Newcombe, 1998](#)).

### **PASI score over time**

Summary statistics will be provided for absolute PASI scores as well as for percent change from baseline by visit and treatment group. Figures will also be provided.

### **IGA mod 2011 score over time**

Summary statistics for the IGA mod 2011 score over time will be presented by visit and treatment group in contingency tables.

### **Relapse**

This analysis will be the same as for “subjects who were PASI 75 responders at Week 52”

### **Rebound**

This analysis will be the same as for the “subjects who were PASI 75 responders at Week 52”

## **Subjects who were partial responders at Week 52**

### **PASI 50, PASI 75, PASI 90, PASI 100 and IGA 0 or 1 response over time**

Summary statistics for PASI 50, PASI 75, PASI 90, PASI 100 and IGA 0 or 1 response by visit will be presented in contingency tables and will include absolute and relative frequencies. Confidence intervals for response rates will be derived as well based on the score method including continuity correction ([Newcombe, 1998](#)).

### **PASI score over time**

Summary statistics will be provided for absolute PASI scores as well as for percent change from baseline by visit and treatment group. Figures will also be provided.

### **IGA mod 2011 score over time**

Summary statistics for the IGA mod 2011 score over time will be presented by visit and treatment group in contingency tables.

### **Relapse**

This analysis will be the same as for the “subjects who were PASI 75 responders at Week 52”

### **Rebound**

This analysis will be the same as for the “subjects who were PASI 75 responders at Week 52”

## **9.5.2 Safety variables**

All safety evaluations will be performed on the Safety set. For adverse events an analysis based on pooled treatment groups “any secukinumab 150 mg” and “any secukinumab 300 mg” will also be done. In the analysis of the subjects who were re-treated after relapse with secukinumab 150 mg or 300 mg only safety data after re-treatment after relapse will be reported. With the exception of adverse events that qualify as "treatment emergent" (see definition below), data collected from telephone visits and unscheduled visits in follow-up period 2 will only be included in individual patient listings, but not in summary tables.

### **Adverse events**

Treatment emergent adverse events are defined as any events started after the first dose of study treatment and within 84 days after the last study treatment, or events present prior to the first dose of study treatment, but increased in severity based on preferred term within 84 days after the last study treatment.

AEs will be summarized by presenting, for each treatment group, the number and percentage of subjects having any AE, having an AE in each primary system organ class and having each individual AE (preferred term). Summaries will also be presented for AEs by severity and for study treatment related AEs. If a subject reported more than one adverse events with the same preferred term, the adverse event with the greatest severity will be presented. If a subject reported more than one adverse events within the same primary system organ class, the subject will be counted only once with the greatest severity at the system organ class level, where applicable.

Confidence intervals for relative frequencies will be derived as well according to the score method including continuity correction by [Newcombe, 1998](#).

Separate summaries will be provided for death, serious adverse event, other significant adverse events leading to discontinuation and adverse events leading to dose adjustment (including study treatment discontinuation).

A graphical display of relative frequencies within system organ classes and relative risks, if appropriate, will be presented.

For infections, time-to-event analysis will be done. Results will be tabulated and the Kaplan-Meier estimates for the cumulative rate will be plotted.

Additional analyses will be provided for adjudicated adverse events.

In supplementary analyses, exposure (or observation)-time adjusted analyses in terms of incidence rate and event rate will be provided.

### **Laboratory data**

The summary of laboratory evaluations will be presented for three groups of laboratory tests (hematology, serum chemistry and urinalysis). Descriptive summary statistics for the change from baseline to each study visit will be presented. These descriptive summaries will be presented by test group, laboratory test and treatment group. Change from baseline will only be summarized for subjects with both baseline and post baseline.

For each parameter, the maximum change from baseline within each study period will be analyzed analogously.

In addition, shift tables will be provided for all parameters to compare a subject's baseline laboratory evaluation relative to the visit's observed value. For the shift tables, the normal laboratory ranges will be used to evaluate whether a particular laboratory test value was normal, low, or high for each visit value relative to whether or not the baseline value was normal, low, or high. These summaries will be presented by laboratory test and treatment group. Shifts will be presented for most extreme values post-baseline.

### **Immunogenicity**

Summary statistics for baseline, each post-baseline visit and change from baseline to each visit will be provided. Summary statistics will be provided for the percent of subjects with immunogenicity. If appropriate, shift tables will also be presented.

### **Vital signs**

Analysis of the vital sign measurements using summary statistics for the change from baseline for each post-baseline visit will be performed. These descriptive summaries will be presented by vital sign and treatment group. Change from baseline will only be summarized for subjects with both baseline and post-baseline values.

### **ECG**

Summary statistics will be presented for ECG variables by visit and treatment group.

### 9.5.3 Health-related Quality of Life (HRQoL)

#### EQ-5D®

The EQ-5D® is a questionnaire with 5 questions (regarding mobility, self-care, usual activities, pain/discomfort, and anxiety/depression) each with three categories (no problem, moderate problem, severe problems) and a health state assessment from 0 (worst possible health state) to 100 (best possible health state). The number and percentage of subjects in each of the three categories for each question will be presented by visit and treatment group. Summary statistics will be shown for the health state assessment by visit and treatment group.

#### DLQI®

The DLQI® measures functional disability of subjects with dermatological disorders that are greater than 18 years of age and had been utilized as a relevant clinical measure in atopic dermatitis, as well as other dermatitis clinical trials. The DLQI® is a simple, validated, self-administered 10-item questionnaire. The instrument contains six functional scales (i.e., symptoms and feeling, daily activities, leisure, work and school, personal relationships, treatment). For the DLQI®, each question will be answered with the following response: “not at all,” “a little,” “a lot,” or “very much”. Seven scores will be derived from the DLQI®: the total score of each of the six dimensions as well as the total score over all items. The higher the score, the more quality of life is impaired.

For each of the seven scores the percentage change from baseline will be derived. Summary statistics will be provided for absolute values as well as for the percentage change by visit and treatment group.

For the “subjects who were PASI 75 responders at Week 52” the following analysis will be performed as well:

The absolute value and the percentage change from baseline of DLQI® total score will be analyzed with the Van-Elteren test using type-II weights, for all pairwise comparisons between secukinumab treatment groups versus placebo. The Van-Elteren test will be performed at each visit. Language of the questionnaire and body weight stratum will be the strata adjusted for in the Van-Elteren test. In addition, stratified Hodges-Lehmann estimates for the median as well as confidence intervals will be derived for the absolute values and percentage change to baseline for each treatment group as well as for all pairwise comparisons between secukinumab treatment groups versus placebo.

It is understood that conclusions obtained from the confidence intervals of these estimates (mean or Hodges-Lehmann estimates for the median) will not be completely consistent with the testing results (Van-Elteren test) which constitute the key analysis for drawing conclusions.

In addition, summary statistics will be provided for number of subjects achieving DLQI 0 or 1. For the “subjects who were PASI 75 responders at Week 52” the secukinumab treatment groups will be compared to placebo by means of Fisher’s exact test.

[figure not shown]

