### **For the subjects classified as PASI 75 responders at Week 52**

Once investigator or designee has entered Week 52 PASI response status in the IRT and also registered with IRT the completion of Week 52 visit of the core studies on secukinumab treatment, a subject will be eligible for randomization in the extension study.

The Week 52 visit in the core study is the randomization visit for CAIN457A2302E1 (extension study).

Based on the fulfillment of inclusion/exclusion criteria by the subject and IRT notification from the database of core studies at Week 52 (explained above), the investigator (or designee) will call the IRT set up of extension study (CAIN457A2302E1). The IRT can be contacted via the Interactive Voice Response System (IVRS) or Interactive Web Response System (IWRS). The IRT will assign a randomization number to the subject, which will be used to link the subject to a treatment groups (secukinumab 150 mg or placebo secukinumab 150 mg or secukinumab 300 mg or placebo secukinumab 300 mg) and will specify a unique medication number for the first package of investigational treatment to be dispensed to the subject. The randomization number will not be communicated to the caller or any of the site staff members.

The randomization numbers at Week 52 will be generated using the following procedure to ensure that treatment assignment is unbiased and concealed from subjects and investigator staff. A subject randomization list will be produced by the IRT provider using a validated system that automates the random assignment of subject numbers to randomization numbers. These randomization numbers are linked to the different treatment groups, which in turn are linked to medication numbers. A separate medication list will be produced by or under the responsibility of Novartis Drug Supply Management using a validated system that automates the random assignment of medication numbers to packs containing the investigational drug(s).

Randomization will be stratified by geographical region and by body weight (< 90 kg or ≥90 kg) collected at Week 52.

The randomization scheme for subjects will be reviewed and approved by a member of the Audit Readiness, Validation & Randomization Group within IIS IA&R (Integrated Information Science Integrated Analytics and Reporting).

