## 9 Data analysis

Treatment groups for analysis will include:

- **Subjects who were PASI 75 responders at Week 52**
  - Secukinumab 150 mg
  - Secukinumab 300 mg
  - Placebo (secukinumab 150 mg in core studies)
  - Placebo (secukinumab 300 mg in core studies)
- **Subjects who were re-treated after relapse with secukinumab 150 mg or 300 mg**
  - Secukinumab 150 mg
  - Secukinumab 300 mg

- Subjects who were partial responders at Week 52
  - Secukinumab 150 mg
  - Secukinumab 300 mg

For open-label period analyses subjects being switched from 150 mg to 300 mg will be summarized as well.

NOTE: Week 52 assessments refer to Baseline extension assessments

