In general, a baseline value refers to the last measurement made prior to administration of the first dose of study treatment. However, for patient reported outcomes (e.g. patient's assessment of PSA pain), lab, ECG, if no pre-treatment value exists a value recorded after first dose can also be used as baseline if it was collected on the same day as first dose.

For efficacy analyses, core baseline will be used for PASI and IGA related variables, such as PASI response, PASI score, et al. Extension baseline will be used for PRO variables.

For safety analyses, extension baseline will be used for all safety variables if not specified.

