#### Table 1-5 Overview of analysis methods for efficacy variables

Variable(s)	Summary statistics for binary/ categorical data	Cochran- Mantel- Haenszel test	Logistic regression	Summary statistics for continuous data	Time-to- event data analysis	Graphs
PASI 50/75/90/100 over time	Х	Х	Х			X 
Loss of PASI 75 response over time during RW period	Х				Х	
Loss of IGA 0 or 1 response over time during RW period	Х				X	
Absolute PASI score over time				х		
% change PASI over time				Х		
IGA mod 2011 0 or 1 response over time	Х	Х	Х			
IGA mod 2011 score over time by categories				Х		
Relapse	Х				Х	Х
Rebound	Х					
EQ-5D	Х			х		
Absolute DLQI 				х		
% change DLQI 				Х		
DLQI 0 or 1 achievement	Х					
HAQ-DI score over time				X 		
HAQ-DI response over time	X 	T				

only for subjects who were PASI 75 responders at Week 52

only for subjects with psoriatic arthritis at baseline

additional analyses for subjects who were PASI 75 responders at Week 52 described below

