## **Dermatology Life Quality Index**

The DLQI© measures functional disability of subjects with dermatological disorders that are greater than 18 years of age and had been utilized as a relevant clinical measure in atopic

Novartis	Confidential	Page 51
RAP Module 3	9-Apr-2018 (1:15)	Secukinumab / AIN457A2302E1

dermatitis, as well as other dermatitis clinical trials. The DLQI© is a simple, validated, selfadministered 10-item questionnaire. The instrument contains six functional scales (i.e., symptoms and feeling, daily activities, leisure, work and school, personal relationships, treatment). For the DLQI©, each question will be answered with the following response: "not at all," "a little," "a lot," or "very much". Seven scores will be derived from the DLQI©: the total score of each of the six dimensions as well as the total score over all items. The higher the score, the more quality of life is impaired.

For each of the seven scores the percentage change from extension baseline will be derived. Summary statistics will be provided for absolute values as well as for the percentage change by visit and treatment group.

In addition, summary statistics will be provided for number of subjects achieving DLQI 0 or 1.

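### The placebo comparison of absolute DLQI total score does not adjust for Week 52 DLQI, and the SAP neither describes the protocol's DLQI test nor says how a Week 52 score of 0 is handled

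*Protocol*

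**What the plan says.** For subjects who were PASI 75 responders at Week 52, Protocol 9.5.3 (DLQI) names two outcomes for testing, "The absolute value and the percentage change from baseline of DLQI" total score. Both go to a "Van-Elteren test using type-II weights, for all pairwise comparisons between secukinumab treatment groups versus placebo", at every visit. On stratification: "Language of the questionnaire and body weight stratum will be the strata adjusted for in the Van-Elteren test". The protocol adds stratified Hodges-Lehmann estimates and says that DLQI conclusions rest on the Van Elteren result. Week 52 DLQI is named neither as a covariate nor as a stratum.

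The SAP fixes the baseline. SAP 1.5.3 states: "Extension baseline will be used for PRO variables". SAP 1.9.10 states: "For each of the seven scores the percentage change from extension baseline will be derived". This agrees with the note that opens Protocol section 9: "NOTE: Week 52 assessments refer to Baseline extension assessments".

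On whether the test survives into the final analysis, SAP 1.1 includes DLQI among the summaries and analyses to be re-run for the randomized withdrawal (RW) period, and its tables of analysis by period and of variables agree. Footnote 4 to the overview of efficacy methods (SAP 1.9.1.3) promises "additional analyses for subjects who were PASI 75 responders at Week 52 described below". The DLQI text in SAP 1.9.10 contains only summary statistics. The list of changes from the protocol (SAP 1.1.1) does not mention the DLQI tests.

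**The concern.** Week 52 DLQI is measured before randomisation into the extension and is already in the database. Differences between subjects that existed at Week 52 are not caused by the randomised treatment. A test of the later absolute score that does not condition on them carries that variation as noise.

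The plan adjusts in this way elsewhere. The Cox model for loss of PASI 75 response includes both the core-study and the Week 52 PASI, and the visit-wise logistic models for PASI and IGA response include baseline PASI. DLQI against placebo is a secondary objective, yet its absolute-score test has no comparable adjustment.

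Percentage change does use the baseline, but by dividing by it and not as a covariate. It cannot be computed when the Week 52 score is 0. Zeros are to be expected in subjects selected for good skin response, and the plan itself treats a DLQI of 0 or 1 as an endpoint. Neither Protocol 9.5.3 nor SAP 1.9.10 says whether such subjects are dropped or handled otherwise.

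At stake are some avoidable loss of precision in one secondary comparison, an undefined outcome for an unknown share of subjects, and a SAP that does not tell the programmer which DLQI test to run.

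**Working it through.** **What the documents supply.** The planned sizes per dose are 276 on secukinumab and 138 on placebo, 414 in all (Protocol 9.7, SAP 1.11). The only power figure concerns the primary endpoint: more than 90% with about 400 subjects for 10% against 23% losing response, at one-sided 2.5%. It reproduces:

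- Hazard ratio: ln(0.90)/ln(0.77) = 0.403.
- Expected events: 276 × 0.10 + 138 × 0.23 = 59.3.
- Schoenfeld power: Φ(√(59.3 × 2/9) × |ln 0.403| − 1.96) = 91.0%.

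This says nothing about DLQI. No DLQI standard deviation, effect size, correlation or power is given, so everything below is conditional.

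**Normal-theory size.** Let r be the correlation between Week 52 DLQI and DLQI at a later visit (assumed 0.3 to 0.7). Relative to the unadjusted absolute score, the variance factor is 1 − r² with baseline as covariate and 2(1 − r) for a simple change score. A comparison with 80% power unadjusted (also assumed) would have adjusted power Φ((1.960 + 0.842)/√(1 − r²) − 1.960).

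| r | 1 − r² | Fall in variance | Adjusted subjects matching 414 unadjusted | 80% power becomes | Change score, 2(1 − r) |
|---|---|---|---|---|---|
| 0.3 | 0.91 | 9% | 377 | 84% | 1.4 |
| 0.5 | 0.75 | 25% | 311 | 90% | 1.0 |
| 0.7 | 0.51 | 49% | 212 | 98% | 0.6 |

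A simple change score beats the absolute score only when r exceeds 0.5. It never beats covariate adjustment, because (1 − r²)/(2(1 − r)) = (1 + r)/2, which is below 1.

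**Simulation closer to the planned test.** The formula above is for means of normal data; the planned test ranks a bounded integer score within strata. A simulation used 276 against 138 subjects, 12 assumed languages each lying within one of 4 regions, two weight strata, skewed integer scores from 0 to 30, and 1,500 trials per setting. Here r is the correlation of the underlying continuous variables before conversion to scores. The baseline-adjusted test applied the same stratified rank statistic to the residuals of ranked follow-up score on ranked Week 52 score. Percentage change was tested only in subjects with a Week 52 score above 0; under the assumed distribution about 54% had a score of 0.

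| r | Absolute score, as planned | Baseline-adjusted | Percentage change |
|---|---|---|---|
| 0.3 | 0.671 | 0.685 | 0.334 |
| 0.5 | 0.657 | 0.719 | 0.407 |
| 0.7 | 0.680 | 0.841 | 0.553 |

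The Monte Carlo standard error of one such figure is about √(0.67 × 0.33/1500) = 0.012, so the difference at r = 0.3 is hardly distinguishable from nothing. From the same starting powers, the normal-theory formula would give 0.712, 0.779 and 0.925. The simulated gains are smaller at every r, and the normal-theory column should be read as optimistic.

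The low power for percentage change depends heavily on the assumed 54%. It shows how much the missing rule could matter, and does not estimate the loss in this trial.

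**Region.** Adding region as a further stratum left the power of the absolute-score test unchanged: 0.671, 0.657 and 0.680 as before, and 0.684 with and without region when region was given an effect. This must be so when each language lies within one region, since region then creates no new strata.

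**The case against.** **The baseline is not ignored.** A reader might infer that the DLQI comparison disregards Week 52 DLQI altogether. The documents do not support that: the same sentence of Protocol 9.5.3 also tests percentage change, and the SAP takes that change from Week 52. This objection stands. The gap is confined to the absolute-score test and to the way percentage change uses the baseline.

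**Region and language.** The protocol states "Randomization will be stratified by geographical region and by body weight", and region is absent from the DLQI strata. A reader might infer lost precision, or that language should be dropped in favour of region. Neither follows. The documents give no breakdown of language by region, language may well be a finer proxy for region, and the simulation showed no gain from adding region under nesting. Stratifying a questionnaire by its language version is defensible. Sparse language strata are possible but cannot be shown.

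**The size is assumed.** This is true of r, of the 80% starting power and of the simulated score distribution. Only the direction is certain: some loss when r is not 0, negligible when r is small.

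**Changing the test is not free.** The SAP governs a final analysis that repeats earlier work, and the sponsor was to be unblinded after Week 68 (Protocol 5.4 and 9.6). Replacing the protocol's named test at that stage would be a post-unblinding change of method. This stands and shapes the fix: add beside the planned test, do not replace it.

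**The SAP may carry the test by reference.** SAP 1 and 1.1 point to section 9 of the protocol, so silence in SAP 1.9.10 does not prove that the test was dropped. That is fair. But a footnote promising a description that never comes leaves the matter open.

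**Conclusion.** The point holds in a limited form. The absolute-score Van Elteren test leaves a collected pre-randomisation value unused and loses some precision whenever Week 52 and later DLQI are correlated. For assumed correlations of 0.3, 0.5 and 0.7, the simulated gain from adjustment was about 1, 6 and 16 percentage points of power (0.685 − 0.671, 0.719 − 0.657, 0.841 − 0.680). None of these sizes can be derived from the documents.

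Two parts need no assumption. The plan has no rule for percentage change when the Week 52 score is 0, and the SAP promises DLQI analyses that it does not describe.

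The consequence is small. The comparison is secondary and outside the multiple-testing strategy. Omitting a baseline covariate does not bias a randomised comparison, so it would be wrong to read this as a challenge to the validity of the DLQI result.

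**What to change.** In SAP 1.9.10:

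1. State that the protocol's Van Elteren test, with its strata and Hodges-Lehmann estimates, is run for PASI 75 responders in the RW period, so that footnote 4 has the text it refers to.
2. Add a rank analysis of covariance of absolute DLQI total score with Week 52 DLQI as covariate, comparing each dose with its own placebo group, stratified by body weight and by either region or language.
3. State how a Week 52 score of 0 is handled for percentage change, and report how many subjects in each group are affected.

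The cost is a few sentences and one more standard analysis of data already collected. The added analysis should be labelled supportive, because it would enter the plan after the sponsor's planned Week 68 unblinding. The protocol's prespecified test keeps its role.
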